5.3 End of research visit (M24)

The last visit is scheduled at month 24 from first GFR measurement, during a one-day hospitalization with mGFR, serum creatinine and proteinuria evaluation at the same exams as in the previous visits.

Expected length of participation and description of the chronology and duration of the research.

Maximum	period	between	selection	and	15 days min

inclusion Inclusion period The included subjects' length of participation:	24 months
Treatment period:	4 months
Follow-up period:	24 months+ 21 days max
Total research period:	48 months

5.4 Table or diagram summarising the chronology of the research

Actions	Inclusion	D0	M2 M4	M6 M9	M12	M18	End of research M24
Visit	Consultation*	hospitalization*	consultation	consultation	hospitalization**	consultation	Hospitalization***
History	Х						
Clinical exam, Medical Interview	x	х	x	x	x	x	х
Inclusion/ Exclusion criteria	x						
Informed consent, randomization	x						
Measured GFR (or estimated)		х	eGFR	eGFR	x	eGFR	Х
Tests (biochemistry, haematology)		х	Х	x	х	x	х
Biological collection (blood, urine)****	X(if control group and mDFG not available)	х			x		x
Sample for PK (5ml)		X (D0,D1,D2)	Х				
Dispensation of treatments		X	X (M2)				
Renal biopsy					Х		
SF36 scale					Х		X
Compliance CT		X	Х				
Compliance RAS	Х	X	X	X	Х	Х	X

Adverse	×	×	×	Y	×	Y
events	~	~	^	^	~	^

* D0: for the control group, 1 one-day hospitalization (= 1 HDJ) if mDFG is available or only consultation (= inclusion/randomisation visit) if mDFG is not available and for the experimental group 3 one-day hospitalizations (=3 HDJ)

** 2 days hospitalization (= 2HC) if biopsy is perfomed and 1 one-day hospitalization (1 HDJ) if mGFR is measured, or only 1 consultation if biopsy is not perfomed and mGFR is not measured

1 one-day hospitalization (= 1 HDJ) or only 1 consultation if mGFR is not measured * DNA sample will be obtained from one of blood samples of biological collection at D0 for control group.

During the first year, the delay accepted to organise every visit is ± 1 week. During the second year, the delay accepted to organise every visit is ± 1 month.

5.5 Distinction between care and research

TABLE: Distinction between procedures associated with "care" and procedures added because of the "research"

	Procedures and treatments associated with care	Procedures and treatments added because of the research
Treatments	RAS blockade	Corticosteroid treatment
Measured GFR		Day 0, Month12, Month 24
Blood and urinary samples	Month 2, 4, 6, 9, 12,18, 24	Biological collection: D0, Month 12, Month 24 Pharmacocinetic: D0, D1, D2, M2, M4
SF36 scale		Month12, Month24
Renal biopsy	Diagnosis renal biopsy	Month 12

5.6 Biological Collection

The samples (blood bank, urine bank, DNA bank) taken as part of the research will be included in a biological collection, stored at -80°C on site for urine and -20°C for DNA - blood bank. All samples sent at the end of the research by agreed transporter.

The collections will be stored:

Type of sample	Quantity	Storage location	Collection supervisor	Purpose of the collection	Storage period (years)	Outcome (destruction, etc.)
urine	D0, M12, M24: 2*15ml	Plateforme Ressources Biologiques H. Mondor	Pr [name] [name]	To identify urinary prognosis markers of failure at 24 months.	20	destruction
blood	D0: 2*7 ml M12, M24: 3*7ml	Plateforme Ressources Biologiques H. Mondor	Pr [name] [name]	To identify seric prognosis markers of failure at 24 months.	20	destruction
cells for DNA extraction	D0: 1*5ml	Laboratoire pharmacocinétique de Cochin	Pr [name]	To identify genetic markers of failure of treatment	20	destruction

The samples may be used with the explicit agreement of the subject on the consent form for further analyses not included in the protocol and which could be beneficial for the IgA nephropathy based on evolution in scientific knowledge.

At the end of the research, the samples will be preserved. The collection will be declared to the minister responsible for research [and to the director of the regional health authority with local jurisdiction if the entity is a health establishment] (Article L. 1243-3 of the CSP (French Public Health Code). All these samples (urine, blood, DNA) associated with research are under the responsibility of the sponsor of this research (APHP).

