4.1.2 Secondary assessment criteria

Failure at 6 months will be defined as:

- PCR > 0.75 g/g
- or PCR > 0.5 g/g and > 30% of initial PCR
- or eGFR < 80% of initial eGFR
- or ESRD
- or renal transplantation
- or death.

Failure at 12 months will be defined as:

- PCR > 0.75 g/g
- or PCR > 0.5 g/g and > 30% of initial PCR
- or mGFR < 80% of initial mGFR (or eGFR if unavailable)
- or ESRD
- or renal transplantation
- or death.

Histological lesions evolution at 12 months :

The evolution of histological lesions will be assessed as the proportion of patients of both therapeutic groups with persistent severe histological lesions in repeat kidney biopsy at 12 months.

GFR evolution (mGFR or eGFR if unavailable):

The evolution of GFR at 12 and 24 months will be assessed as:

- the absolute value of GFR
- the absolute difference of GFR from the baseline
- the annual degradation (ml/min/1,73m²/year) of GFR during the 24 months

Proteinuria evolution

The evolution of proteinuria will be assessed as:

- the absolute value of proteinuria at 12 and 24 months
- the absolute difference of proteinuria from baseline at 12 and 24 months

Identification of prognosis markers of failure at 24 months:

Clinical, histological, and biological data (including PCR ratio, eGFR and mGFR, renal histological lesions) will be compared between patients with or without failure.

Comparison of side effects in each therapeutic group.

Comparison of life quality scale in each therapeutic group with SF36 scale at 12 and 24 months

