4.2 Description of research methodology

4.2.1 Experimental plan

Phase III, prospective, multicenter, randomized open-labelled study.

Included patients will be randomized according to a 1:1 ratio:

- early corticotherapy + RAS blockade (experimental group)

or

- RAS blockade alone (control group), with corticosteroids in case of failure at 6, 9, 12 or 18 months or in case of rapid deterioration of renal function at 2 months and proposed corticosteroids in case of failure at 4 months.

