8 ASSESSMENT OF EFFICACY

Proteinuria/creatininuria ratio (PCR) and eGFR (CKD-EPI formula) evaluation

Serum creatinine will be evaluated with an enzymatic IDMS-traceable assay. Urinary protein, creatinine, sodium and urea will be evaluated on a 24-hour urinary collection (or urinary sample) at each visit.

Biochemistry analyses can be performed in private practice laboratories.

In case of failure, Proteinuria and eGFR will be re-evaluated on a second sample, within an interval of at least 14 days. For each visit, the final GFR and PCR value will be calculated from the second dosage.

Histological lesions evaluation

Renal biopsy will be performed and processed according to local practices. Histologic assessment will be performed according to the Oxford criteria studies. For patient inclusion, each inclusion criterium (mesangial proliferation, endocapillary proliferation, focal segmental glomerulosclerosis, tubular atrophy/interstitial fibrosis, cellular/fibrocellular crescents) will be scored by local pathologists. Secondarily, all renal biopsies will be re-evaluated *a posteriori* in the Necker pathology department.

Measured GFR evolution will be evaluated as follows:

mGFR will be performed according to local practice (iohexol clearance, inuline clearance, CrEDTA clearance, ...).

Given that the randomization is stratified by centre, the difference between the mGFR techniques should not have a major effect in data interpretation.

Identification of prognosis markers of failure at 24 months:

These factors will include (but are not restrited to):

- clinical factors (blood pressure, history of macroscopic haematuria, familial history of IgAN),
- biological factors (initial and time-average proteinuria, initial eGFR, time-average sodium chloride consumption),
- renal histological lesions evaluated *a posteriori* (oxford criteria, thrombotic microangiopathy, focal segmental glomerulosclerosis with features of podocytopathy)

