9 STATISTICAL ASPECTS

9.1 Calculation of sample size

Given the results of previous studies, we assume that 60% of the patients in the control group will achieve the failure criteria at 24 months. We aim to obtain a decrease to 35% of failure with early corticotherapy (i.e in the experimental group). With 80% power and an 2-sided alpha risk equal to 5%, 61 subjects per group are required. Consequently, 122 patients will be included in this study.

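### The 24-month prognosis-marker objective draws on post-randomisation and M24 data and compares failures with non-failures without a stated treatment term

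*Protocol*

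**What the plan says.** Identifying prognosis markers of 24-month failure is a listed secondary objective (Protocol 3.2). Four places define it.

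- Section 4.1.2 gives the method: "Clinical, histological, and biological data (including PCR ratio, eGFR and mGFR, renal histological lesions) will be compared between patients with or without failure".
- Section 8 lists candidates, among them "biological factors (initial and time-average proteinuria, initial eGFR, time-average sodium chloride consumption". Baseline and follow-up quantities stand side by side.
- Section 5.6 sets urine collection as "D0, M12, M24: 2*15ml", with the purpose "To identify urinary prognosis markers of failure at 24 months". Blood is taken at the same three visits with the matching serum purpose. The purpose is not separated by visit.
- Section 9.2 names chi-square or Fisher and t or Wilcoxon tests for secondary efficacy and safety end points. It gives no method specific to markers. The only models for which it states a treatment term are the subgroup models of the primary outcome.

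Section 4.1.1 defines failure at 24 months partly by the PCR and the GFR change at that time.

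**The concern.** A prognosis marker has to be known before the outcome it predicts. A sample from the M24 visit describes a patient whose failure status is being determined at that visit. Whatever it shows is a correlate of being in failure, not a forecast of it.

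The second problem concerns every marker measured after randomisation. The trial is designed on the premise that treatment lowers failure, so arm is expected to be associated with failure. If treatment also shifts a marker, patients without failure will carry more of the shifted values simply because more of them are in the experimental arm. A comparison by failure status that ignores arm then finds a difference even when the marker says nothing about outcome within either arm.

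At stake is the interpretation of the marker results and the use of a biobank kept for 20 years. Markers of treatment received, or of current failure, could be reported as prognosis markers.

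**Working it through.** **Inputs from the protocol (9.1 and 4.2.1).** Control failure 60% ("we assume that 60% of the patients in the control group will achieve the failure criteria at 24 months"); experimental failure 35% ("We aim to obtain a decrease to 35% of failure with early corticotherapy"); size ("With 80% power and an 2-sided alpha risk equal to 5%, 61 subjects per group are required"); 1:1 allocation.

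**Input assumed.** The marker differs by d SD between arms and is unrelated to failure within each arm. The documents give no value for d, so a range is shown.

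**Step 1: the plan's own figure.** With pooled variance, mean rate (0.60 + 0.35)/2 = 0.475, and

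n = [1.96 × √(2 × 0.475 × 0.525) + 0.8416 × √(0.60 × 0.40 + 0.35 × 0.65)]² / 0.25² = (1.384 + 0.575)² / 0.0625 ≈ 61.4 per arm.

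This is 62 when rounded up. The unpooled formula gives 59, and power at 61 per arm is 79.7%. The stated 61 is reproduced and is not in dispute.

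**Step 2: arm mix by outcome.** With equal arms:

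- experimental share of failures = 0.35 / (0.60 + 0.35) = 0.368
- experimental share of non-failures = 0.65 / (0.40 + 0.65) = 0.619
- difference = 0.251
- expected numbers: 61 × 0.95 ≈ 58 failures and 61 × 1.05 ≈ 64 non-failures

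**Step 3: spurious difference.** A marker with no within-arm link to failure differs by 0.251 × d between non-failures and failures. Its SD with the arms mixed is about √(1 + 0.25d²). The standard error is that SD × √(1/58 + 1/64) = SD × 0.181.

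| d | Difference | SD | SE | Ratio | Two-sided p < 0.05, normal approximation | Simulation, arm ignored | Simulation, arm in model |
|---|---|---|---|---|---|---|---|
| 0.5 | 0.125 | 1.031 | 0.187 | 0.67 | 10% | 10.5% | 5.2% |
| 1.0 | 0.251 | 1.118 | 0.203 | 1.24 | 24% | 23.4% | 5.1% |
| 1.5 | 0.376 | 1.250 | 0.227 | 1.66 | 38% | 38.6% | 5.2% |

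The simulations used 6,000 runs per setting with 61 patients per arm. At d = 2 the rates were 50.6% with arm ignored and 5.6% with arm in the model.

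**Step 4: dependence on the treatment effect.** With failure rates of 60% and 50%, ignoring arm gives 7.8% at d = 1 and 12.2% at d = 2. With 50% in both arms it stays near 5% at every d from 0 to 2.

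**Step 5: rescue steroids.** Steps 2 to 4 take the marker shift to follow randomised arm. Under 4.2.1 and 7.4.1, controls who meet interim failure criteria can receive the same course. If the shift follows steroid exposure instead, and a fraction r of failing controls is rescued but no non-failing control is, exposure is 0.368 + 0.632r among failures and 0.619 among non-failures. These are equal at r = (0.619 − 0.368)/0.632 ≈ 0.40. The excess could therefore shrink, vanish or reverse. The protocol gives no expected rescue rate.

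**Step 6: M24 samples.** No arithmetic is needed. Section 4.1.1 reads failure at 24 months, and 5.6 takes the sample at 24 months. No adjustment changes that order.

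**The case against.** The strongest reply is that the protocol does not say the arms are pooled. Section 4.1.2 gives a one-sentence comparison with no model, and the tests in 9.2 are named for efficacy and safety end points. Covariates and landmark times are commonly left to the statistical analysis plan, which is not at hand and may include arm. This stands: a reader might infer that an unadjusted pooled analysis is fixed, but the documents support only that no treatment term is stated. It does not dispose of the point, because 4.1.2, 5.6 and 8 do fix the comparison and the candidate markers, including those measured after randomisation.

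It may also be said that 5.6 is an inventory, so its purpose column is no commitment to test each visit's samples as predictors. That is fair as to intent, but the stated purpose is still wrong for M24. Section 8 has a failing result repeated at least 14 days later. That may place the banked sample shortly before the confirming one, but it does not make the sample a predictor in any useful sense.

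The size is also open to challenge. Oral steroids end at month 4 (7.1), so an M12 or M24 marker must keep its shift for about 8 or 20 months. The documents give no reason to expect a steroid effect on salt intake. Residual proteinuria is already cited as prognostic in 2.2, so it is not a null marker. Rescue in controls may reverse the artefact. All of this stands, and it is why the figures are conditional.

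**Conclusion.** The point holds in two parts of different strength.

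The first rests on the protocol alone: M24 urine and blood cannot serve as prognosis markers of failure at M24.

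The second is conditional. If the comparison in 4.1.2 is run without arm, a marker that differs by arm but has no within-arm link to failure is more likely than 5% to be declared prognostic: about 10%, 24% and 38% at assumed shifts of 0.5, 1.0 and 1.5 SD. This requires the planned 60% v 35% effect and a shift that persists to the sampling visit and follows randomised arm.

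A reader might infer that anything steroids alter will look prognostic. The figures do not support that. At these shifts, 62% to 90% of such markers would not be declared, and there is no inflation if failure rates are equal. Nor are all later samples unusable: M12 samples precede the outcome and can be prognostic in a suitable analysis. D0 samples, DNA and the diagnostic biopsy are unaffected.

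Only a secondary objective of exploratory character is touched. The primary comparison and the sample size stand.

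**What to change.** Amend 4.1.2, 5.6 and 8, and carry the same text into the statistical analysis plan:

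- Define prognosis markers as D0 values, including the diagnostic biopsy, tested in a model of 24-month failure that includes treatment arm.
- Analyse M12 or time-averaged markers only in a landmark analysis using data up to M12, among patients free of ESRD, transplantation and death at M12. Include arm and rescue steroid exposure before the landmark in the model; arm alone does not account for rescue. Stopping the average at M12 also keeps the M24 PCR, which helps define failure, out of the marker. The restriction fits 5.7.3.1, under which patients with ESRD or transplantation have no further protocol visits.
- Relabel M24 samples in the purpose column of 5.6 as concurrent correlates of failure.

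The cost is wording only: no new samples, visits or patients. The downside is that fewer markers will qualify as prognostic, and the landmark analysis will lose patients who reach ESRD, transplantation or death before M12.

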5.7 Termination rules

5.7.1 Criteria and methods for prematurely terminating the experimental treatment

Different situations:

- Temporary termination of treatment, the investigator must document the reason for stopping and restarting the treatment in the subject's source file and the case report form (CRF)
- Premature termination of treatment but the subject is still included in the research, until the end of the subject's participation, the investigator must document the reason.

The investigator must:

- Document the reason(s)
- Collect the assessment criteria when participation in the research ends, if the subject agrees

5.7.2 Follow-up of the subjects after the premature termination of experimental treatment

If a subject stops prematurely the treatment, the subject is still included in the research, until the end of the subject's participation. The subject will have to in minima realize the visits M6, M12 and M24.

Ending a subject's participation does not affect the normal management of the subject's illness in any way.

If there are serious adverse events, the investigator must notify the sponsor and monitor the subject until the end of the research. If treatment is stopped prematurely due to a serious adverse event, a serious adverse event notification form will be sent by [contact]) to the sponsor. The serious adverse event will be monitored until it is resolved.

5.7.3 Terminating part or all of the research

5.7.3.1 Criteria and methods for prematurely terminating all or part of the research by the patient

Any subject can withdraw from participating in the research at any time and for any reason. In case of end stage renal disease (ESRD) or renal transplantation, the subject stay in the research but the patient will not have anymore visits in the protocol. Only infectious AE and SAE will be report.

The investigator can permanently end a subject's participation in the research for any reason that affects the subject's safety or which would be in the subject's best interests.

If the subject is lost to follow-up, the investigator has to make contact with the subject and draw it in the file source to know at least if the subject is alive or died.

If a subject leaves the research prematurely, data relating to the subject can be used.

The case report form must list the various reasons for ending participation in the research:

- □ Explicit withdrawal of consent
- □ Follow- up
- Death
- □ Other

5.7.3.2 Criteria and methods for prematurely terminating all or part of the research by sponsor

AP-HP as sponsor or the Competent Authority (ANSM) can prematurely terminate all or part of the research, temporarily or permanently, in the following situations:

- first of all, if suspected unexpected serious adverse reactions (SUSARs) are seen in an arm being treated or if there is a discrepancy in the serious adverse reactions between the 2 arms, and which require a reassessment of the benefit-risk ratio for the research.
- likewise, if unexpected facts, new information about the product, in light of which the objectives of the research are unlikely to be achieved.
- if it appears that the inclusion objectives are not met.

If the research is terminated prematurely, the decision and justification will be given by the sponsor, AP-HP, to the Competent Authority (ANSM) and to the CPP within 15 days.

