9.2 Description of statistical methods to be used

All statistical analyses will be performed by Dr [name] (Paris Centre Clinical Research Department) using R software (http://cran.r-project.org).

Primary analyses will include all patients who underwent randomization and will be conducted on the intention-to-treat principle for efficacy outcomes and according to treatment received for toxicity end points. A per protocol analysis will be also performed, after exclusion of the subjects with at least one significant protocol deviation.

Descriptive analyses will be done for the two arms of treatment. Continuous variables will be summarized as mean (standard deviation) or median [range] and categorical variables as frequencies and percentages.

Primary end-point

Percentages of patient with failure at 24 months (as defined earlier) will be compared between groups using Chi2 test. Treatment effect will be presented as Relative Risk (RR) and its 95% CI.

Secondary end-points

Secondary efficacy and safety end points were analysed using Chi2 test (or Fisher's test if appropriate) and Student t test (or Wilcoxon test if appropriate).

To explore the emergence of any time-related patterns of response to treatment, means and 95% confidence intervals (CIs) for changes relative to baseline in proteinuria and GFR were plotted vs time from randomization until end of follow-up at 24 months. Means and 95% CIs for changes from baseline were compared at 6, 12 and 24 months using Student t test. In addition linear marginal regression models will be performed, if appropriate.

Three subgroups analyses are planned to explore whether the primary outcome results differed in particular groups of patients. Histological subgroups will be defined as the presence of mesangial proliferation or not, the presence of endocapilary proliferation or not and the presence of cellular or fibrocellular crescents or not. Log binomial regression models will be used for the subgroup analyses and will include terms for treatment group, subgroup, and the interaction between treatment group and subgroup. The interaction terms represent potential subgroup differences in treatment effects.

For efficacy and safety comparisons, P values of less than 0.05 were considered to indicate statistical significance.

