10.3 Specific features of the protocol

All serious and non-serious adverse events must be reported in the CRF.

Serious adverse events that do not require the investigator to notify the sponsor

These serious adverse events are only recorded in the "adverse event" section of the case report form. They include the events associated with:

• Normal and natural evolution of the pathology, for example: High blood pressure, headaches except for the first 2 months of corticotherapy Lower limbs edema except for the first 2 months of corticotherapy Gross haematuria

Acute renal failure

Nephrotic syndrome

Special circumstances

Hospitalization for pre-existing pathology

Hospitalization for a medical treatment or scheduled surgery before the research Admission for social or administrative reason

Hospitalization in an emergency department (<12 hours)

• Adverse events likely to be associated with the treatments prescribed as part of the patient's care during the monitoring of the research, for example adverse events related to the prescription of RAS blockers :

Hypotension

Acute renal failure

Glucose metabolism disequilibrium

Serious adverse events that require the investigator to immediately notify the sponsor

The investigator must report all adverse events that meet one of the seriousness criteria below:

1- Death

- 2- Life threatening situation
- 3- Requiring hospitalization or prolonging hospitalization
- 4- Persistent or significant disability or incapacity
- 5- Congenital abnormality or birth defect
- 6- Or any other adverse event considered "medically significant"

The serious adverse events the most related are:

- High blood pressure (systolic blood pressure ≥180 mmHg or diastolic blood pressure ≥120mmHg), headaches and lower limbs edema in the first 2 months of corticotherapy, diabetes, infections, osteoporosis with fracture and cardiac insufficiency.

Other events that require the investigator to immediately notify the sponsor

• In utero exposure

The sponsor must be notified immediately about any pregnancy during which the foetus (from the pre-embryonic stage up to birth) could have been exposed at a given time to an experimental medication, even if the pregnancy is not associated with an adverse event. Notification is required if the exposure involves the mother.

Other events occurring following an interaction between corticosteroids and antihypertensive treatments (Beta blockers and diuretics):

Hyperkalemia (> 6mmol/l)

Torsade de pointes

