
10.4 Procedures and deadlines for notifying the sponsor

Notification of an SAE must initially be provided in a written report using the special form for reporting SAE. The report must be signed by the investigator.

Each item in the form must be completed by the investigator so that the sponsor can carry out the appropriate analysis.

This initial notification must be followed by one or more detailed follow-up report(s), in writing and signed, within a maximum of 8 days in the case of a fatal or life-threatening event and within 15 days for all other cases.

Whenever possible, the investigator will provide the sponsor with any documents that may be useful (medical reports, laboratory test results, results of additional exams, etc.). These documents must be made anonymous. In addition, the documents must include the following: research acronym, number and initials of the subject, nature and date of the serious adverse event.

Any adverse event will be monitored until fully resolved (stabilisation at a level considered acceptable by the investigator, or return to the previous state) even if the subject has left the trial.

The initial notification, the SAE follow-up reports and all other documents must be sent to the sponsor via fax only to the Vigilance Division of the DRCI, [contact]**.

For this study using e-CRF:

- the investigator completes the SAE notification form in the e-CRF, validates, prints and signs the form before sending it *via* fax.

- if it is not possible to connect to the e-CRF, the investigator will complete, sign and send the SAE notification form. As soon as the connection is restored, the SAE notification form in the e-CRF must be duly completed.

The investigator must comply with all requests from the sponsor for additional information.

For all questions relating to the notification of an adverse event, the Vigilance Division of the DRCI can be contacted via email: [contact]

In utero exposure

The investigator completes the "form for monitoring a pregnancy that developed during a biomedical research" and sends it by fax to the Vigilance Division at **[name]**.

The investigator must monitor the pregnant woman throughout her pregnancy or until the pregnancy is terminated, and must notify the sponsor of the outcome of the pregnancy, using this form.

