10.5 Period for notifying the sponsor

The investigator must report all SAE that occur in research subjects:

- After the date of the first procedure specific to the research

- Throughout the period during which the participant is monitored, as determined by the research

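### After ESRD or transplantation, section 5.7.3.1 ends visits and narrows adverse-event reporting, which contradicts 10.3 and loses SF36 data because of the outcome itself

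*Protocol*

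**What the plan says.** Section 5.7.3.1 of the protocol states that, after ESRD or renal transplantation, the subject remains in the research but "the patient will not have anymore visits in the protocol. Only infectious AE and SAE will be report".

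The safety chapter sets its rules without reference to this case:
- Section 10.3: "All serious and non-serious adverse events must be reported in the CRF".
- Section 10.5: "The investigator must report all SAE that occur in research subjects", for as long as the participant is monitored.
- Section 10.4: "Any adverse event will be monitored until fully resolved", including in subjects who have left the trial.

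Section 4.1.2 lists as secondary criteria a side-effect comparison, SF36 at 12 and 24 months, proteinuria, and GFR, the last including "the absolute difference of GFR from the baseline". Sections 5.2, 5.4 and 5.5 schedule SF36 at months 12 and 24 only. Section 9.2 says: "Means and 95% CIs for changes from baseline were compared at 6, 12 and 24 months using Student t test". For secondary endpoints in general it also allows the Wilcoxon test where appropriate, and it foresees marginal regression models if appropriate.

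**The concern.** Two rules for recording adverse events apply to the same patient, who is still in the research. The narrower rule is also ambiguous: *infectious* may qualify only AE, or both AE and SAE. In an open-label trial with 27 centres and a planned between-arm comparison of side effects, centres could record different things.

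The end of visits also removes SF36. That questionnaire remains answerable on dialysis or with a graft, and nothing done at analysis can recover answers never collected. The data go missing because the patient had a bad renal outcome, so the quality-of-life comparison would describe patients who avoided ESRD. By contrast, section 5.7.2 requires at least the month 6, 12 and 24 visits from patients who merely stop treatment early.

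**Working it through.** **1. The plan's own figure.** Section 9.1 gives 61 per group for 60% against 35% failure, 80% power and two-sided 5%. The pooled-variance formula without continuity correction gives 62, the arcsine formula gives 61.3, and power at 61 per group is 79.7%. The stated size is reproduced. Section 4.1.1 counts ESRD and transplantation as failure, so the primary endpoint needs no visit after either event and the sample size is untouched. The same holds for failure at 6 and 12 months in 4.1.2.

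**2. What is recorded after ESRD or transplantation, rule against rule.**

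| Event type | 5.7.3.1 | 10.3 to 10.5 |
|---|---|---|
| SAE, infectious | reported | reported |
| SAE, non-infectious | reported on the natural reading; not reported if *infectious* also qualifies SAE | reported (10.5) |
| Non-serious AE, infectious | reported | reported (10.3) |
| Non-serious AE, non-infectious, new | not reported | reported (10.3) |
| AE that began before ESRD | already recorded | followed to resolution (10.4) |

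The fourth row conflicts on any reading. The second conflicts on one reading. Section 10.5 ties SAE reporting to the period in which the participant is monitored, and 5.7.3.1 does not say whether a patient without visits is still monitored. The fourth row can include steroid effects: section 7.4.1 allows a four-month rescue course from as late as month 18, so a course can run to about month 18 + 4 = 22.

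**3. SF36.** With assessments at months 12 and 24 only, ESRD before month 12 leaves no SF36 value at all. ESRD between months 12 and 24 loses the month 24 value.

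**4. Number of patients.** Section 2.2 gives 10 to 20% ESRD within 10 years, and 91% renal survival at 45 months of mean follow-up in a retrospective cohort of 703 patients. With a constant hazard (assumed), the risk by month *m* is 1 − S^(*m*/*t*), where S is survival free of ESRD at *t* months.

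| Input | Risk by month 24 | Of 122 | Of 122 by month 12 |
|---|---|---|---|
| 10% in 10 years | 1 − 0.90^(24/120) = 2.1% | 2.5 | 1 − 0.90^(12/120) = 1.0%, 1.3 |
| 20% in 10 years | 1 − 0.80^(24/120) = 4.4% | 5.3 | 1 − 0.80^(12/120) = 2.2%, 2.7 |
| 91% at 45 months | 1 − 0.91^(24/45) = 4.9% | 6.0 | 1 − 0.91^(12/45) = 2.5%, 3.0 |

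So about 2.5 to 6 patients in all (about 1.3 to 3 per arm) would lose some follow-up, and roughly half of them would have no SF36 value.

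**5. GFR, as an illustration only.** If patients with ESRD are left out of the comparison of means, the between-arm difference changes by (k_control − k_experimental) × (loss in ESRD patients − loss in the others)/61. Take 3 against 1 patients, a loss of 8 ml/min/1.73m² in the others, and 25 or 40 in those with ESRD. The shift is 2 × 17/61 = 0.56 or 2 × 32/61 = 1.05. With 6 against 2 and a loss of 40 it is 4 × 32/61 = 2.10. The splits and the losses are assumptions; the protocol gives neither.

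**The case against.** A reader might infer that the worst outcomes drop out of the efficacy and safety evaluation. The protocol does not support that. ESRD, transplantation and death are failures in the primary endpoint and in both intermediate failure endpoints. On the natural reading SAEs are still reported, and 10.3 itself names diabetes and osteoporosis with fracture among the most related serious events. Events that began before ESRD are already recorded and followed. What is lost from the safety comparison is only the new, non-serious, non-infectious event.

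A reader might also infer that ending visits biases the GFR result materially. This is not shown either. Native-kidney GFR and proteinuria lose their meaning after dialysis or a graft, so ending those measurements is no error. How such patients enter the continuous comparisons may be set in an analysis plan that is not at hand, and section 9.2 leaves room for marginal models and rank tests. The shifts in step 5 depend on chosen inputs. Patients may enter with eGFR as low as 20 ml/min/1.73m², and someone entering at 25 cannot lose more than 25, so the smaller shifts are the likelier ones.

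Finally, 5.7.3.1 can be defended as a deliberate exception to 10.3. That answers the contradiction only in part. Section 10.3 carries no exception or cross-reference, the meaning of *infectious* stays open, and SF36 is lost even if the exception is intended.

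**Conclusion.** The point holds in a limited form. The protocol contradicts itself on adverse-event reporting after ESRD or transplantation: with 10.3 on any reading, and with 10.5 on one reading. It also causes an avoidable, outcome-dependent loss of SF36. Neither can be repaired at analysis, because the data would not exist.

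The size is small: about 2.5 to 6 of 122 patients. This assumes a constant hazard and that the background rates apply. The selection of severe lesions could raise the number; the exclusion of eGFR below 20, rapid creatinine rise and very advanced lesions could lower it. The primary analysis, its power and the intermediate failure endpoints do not change. For GFR, no particular bias is established. All that is needed is a stated rule that keeps these patients in the comparison.

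**What to change.** - **Adverse events.** Reconcile 5.7.3.1 with 10.3 to 10.5 so that one rule applies up to month 24 to every patient still in the research. Say outright that all SAEs are reported, infectious or not. Information can be gathered by telephone or from the medical file.
- **SF36.** Collect it at months 12 and 24 by post or telephone after ESRD or transplantation.
- **GFR at months 12 and 24.** Give these patients the worst rank and compare arms with the Wilcoxon test that 9.2 already allows, rather than leaving them out of the t test. Do not use graft GFR or post-transplant proteinuria. No further GFR measurement is needed.

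The cost is amendment wording and a few remote contacts. The GFR comparison then gives a rank-based result, which is less direct to read than a difference in ml/min/1.73m²; the mean change among patients with a measured value can be shown beside it as description.
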